# 9.1 Registry Study Design

FOPal is an observational, prospective and retrospective registry study designed to collect and assess real-world safety data on paediatric and adult participants with FOP exposed to palovarotene and secondly to describe the effectiveness of palovarotene in exposed participants. Additionally, key safety outcomes (i.e. flare-up episodes, growth and bone fractures) will be descriptively compared in participants with FOP exposed and unexposed to palovarotene enrolled in the FOPal registry.

Exposed and unexposed participants will be recruited in countries/sites willing to participate and where palovarotene is registered/marketed. For exposed participants, the decision to prescribe palovarotene will be made prior to and independently of the decision to enrol the patient in the FOPal registry study.

Participants who started palovarotene treatment before the implementation of the registry study in their country may also be enrolled. All participants who received at least one dose of palovarotene treatment before enrolling in the registry study (i.e. signing the informed consent) will be considered non-naïve. In such context, some data will be collected retrospectively from the first dose of marketed palovarotene intake. A schematic representation of the different data collection scenarios is shown Figure 2.

Figure 2 Schematic representation of the different scenarios applied for prospective and retrospective data collection from participants enrolled in the FOPal registry

The schedule of assessments in Table 2 and Table 3 describes the type of data collected for exposed naïve and non-naïve participants, respectively, from the first dose of marketed palovarotene intake. The schedule of assessments in Table 4 describes the type of data collected for unexposed participants from up to 12 months before the ICF signature. The details are described in the Section 9.2.7.

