- o Paper-based patient-reported questionnaires.
- p Retrospective data collected only at the first marketed palovarotene intake.

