# For exposed naïve participants (Table 2)

- Baseline demographics;
- Physical examination including a general assessment as well as dermatologic, lymph nodes, head, eyes, ears, nose and throat (HEENT), chest, cardiac, abdomen, limb/extremities, musculoskeletal, neurologic and other assessments (as per routine clinical care);
- Medical or surgical history (12 months before the Baseline Visit);
- FOP history (date of symptom onset, date of diagnosis by a physician, method of diagnosis, date of genetic test if performed and type of FOP genetic variant);
- Growth status assessment for growing children (bone age, knee height and epiphyseal status assessment);
- Tanner staging for growing children;
- Linear height and weight (linear height within 6 to 12 months prior to the Baseline Visit will also be collected);
- Vital signs (respiratory rate, blood pressure and heart rate);
- Pregnancy test (as per local label, participants are assessed for child-bearing status and pregnancy prevention measures. These conditions also concern participants who are not currently sexually active unless the prescriber considers that there are compelling reasons to indicate that there is no risk of pregnancy);
- Prior (two months before the Baseline Visit) and concomitant medications;
- Concomitant surgery and non-drug therapies;
- Prior use of palovarotene (investigational product);
- Marketed palovarotene dose for chronic and flare-up treatment;
- Spirometry and DLCO test;
- CAJIS for FOP;

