#### For exposed non-naïve participants (Table 3):

- Baseline demographics;
- Physical examination including a general assessment as well as dermatologic, lymph nodes, HEENT, chest, cardiac, abdomen, limb/extremities, musculoskeletal, neurologic and other assessments (as per routine clinical care);
- Medical or surgical history (12 months before the first marketed palovarotene intake);
- FOP history (date of symptom onset, date of diagnosis by a physician, method of diagnosis, date of genetic test if performed and type of FOP genetic variant);
- Growth status assessment for growing children (bone age, knee height and epiphyseal status assessment) at the first marketed palovarotene intake and at the Baseline Visit;
- Tanner staging for growing children at the first marketed palovarotene intake and at the Baseline Visit:
- Linear height and weight from the first marketed palovarotene intake and at the Baseline Visit (linear height within 6 to 12 months prior to the first marketed palovarotene intake will also be collected);
- Vital signs (respiratory rate, blood pressure and heart rate);
- Pregnancy test (as per local label, participants are assessed for child-bearing status and pregnancy prevention measures. These conditions also concern participants who are not currently sexually active unless the prescriber considers that there are compelling reasons to indicate that there is no risk of pregnancy);
- Prior (two months prior to the first marketed palovarotene intake and until the Baseline Visit) and concomitant medications;
- Concomitant surgery and non-drug therapies;
- Prior use of palovarotene (investigational product);
- Marketed palovarotene dose for chronic and flare-up treatment;
- Spirometry and DLCO test at the first marketed palovarotene intake and at the Baseline Visit:

PAGE 47 OF 287

- CAJIS for FOP at the first marketed palovarotene intake and at the Baseline Visit;
- Movement mobility history, including flare-ups (over the past 12 months prior to the first marketed palovarotene intake and until Baseline Visit);
- Movement mobility changes, including flare-ups (from Baseline Visit);
- Spinal health assessment using radiological imaging (e.g. CT, X-ray, scintigraphy, etc) at the first marketed palovarotene intake and at the Baseline Visit;
- Retrospective important medical events related to the disease (including vertebral fractures) at the first marketed palovarotene intake and until the Baseline Visit;

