**PAGE 55 OF 287** 

#### 9.3.2.8 Effectiveness Variables

Cumulative Analogue Joint Involvement Scale

The CAJIS for FOP will be collected at the Baseline Visit and at the Follow-up/End of Study Visits (only if a clinic visit) if available.

The CAJIS is an objective measure of joint movement completed by the investigator to document total joint involvement [36]. This scale, which was developed by the investigators from the Center for Research in FOP and Related Disorders, assesses functional disability by categorising ROM across 12 joints (both right and left shoulder, elbow, wrist, hip, knee and ankle joints) and three body regions (cervical spine, thoracic/lumbar spine and jaw), with each joint/region assessed as: 0=normal (<10% deficit); 1=partially impaired (10% to 90% deficit); 2=functionally ankylosed (>90% deficit). The CAJIS total score is calculated as the sum of the scores of all joints/regions and ranges from 0 (no involvement) to 30 (maximally involved).

The examiner must also note and record (yes/no) if the participant:

- Can walk;
- Uses a wheelchair;
- Needs some help with activities of daily living;
- Needs complete help with activities of daily living.

Use of Assistive Devices and Adaptations for Daily Living

The use of assistive devices and adaptations for daily living will be collected at the Baseline Visit and at the Follow-up/End of Study Visits if available.

The questionnaire will be filled in by the participant or the proxy as per below table:

Questionnaire	If participant is an Adult (≥15 years)	If participant is a Child (<15 years) Filled by	
	Filled by		
	Participant	Participant	Proxy
FOP assistive devices assessment (Version 1.0)	X*		X

\* If participants are unable to answer on their own, an individual can be involved and reports only the participant's response on their behalf.

FOP=Fibrodysplasia Ossificans Progressiva.

In case of PRO completion by an individual (if participants are unable to answer on their own), the recommendations for such administration are detailed below:

- The individual should be different from a healthcare professional and should be the same across multiple assessments.
- The individual must only report the participant's response without any amendments or interpretation.

Assistive devices and adaptations for daily living (including healthcare utilisation) include:

- Mobility aids;
- Eating tools;
- Personal care tools;
- Bathroom aids and devices;
- Bedroom aids and devices;

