# 9.7.3.3 Analysis of Secondary Endpoints – Effectiveness Evaluation

Effectiveness data will be included in the participant data listings using the Safety Exposed and the Safety Unexposed Populations. Analyses and summary tables will be presented in the Safety Exposed and the Safety Unexposed Populations.

Data will be tabulated descriptively, i.e. the number and percentage of participants for each category for categorical parameters and the number, mean, standard deviation, 95% CIs of the mean/median when appropriate, median, minimum and maximum for continuous parameters will be tabulated.

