**PAGE 62 OF 287** 

Cumulative Analogue Joint Involvement Scale

Actual values as well as the change from the Baseline Visit in CAJIS total score will be presented for each visit.

Actual values as well as the shift from the Baseline Visit in ambulation and use of assistive devices/adaptations for daily living will also be presented for each visit.

Use of Assistive Devices and Adaptations for Daily Living

Actual values as well as the shift from the Baseline Visit in the use of assistive devices and adaptations for daily living will be presented for each visit.

Fibrodysplasia Ossificans Progressiva-Physical Function Questionnaire

The FOP-PFQ consists of 28 questions in the adult version and 26 questions in the paediatric version which are scored on a scale of 1 to 5.

The total score will be calculated as follows:

- Adult version: the sum of the scores from each question which will range from  $28 \times 1 = 28$  to  $28 \times 5 = 140$ ;
- Paediatric version: the sum of the scores from each question which will range from  $26 \times 1 = 26$  to  $26 \times 5 = 130$ .

The upper extremities subscore will be calculated as follows:

- Adult version: the sum of the scores from 15 questions (Questions 1-12, 14, 25 and 26) which will range from  $15 \times 1 = 15$  to  $15 \times 5 = 75$ ;
- Paediatric version: the sum of the scores from 18 questions (Questions 1, 2, 6-11, 16-19 and 21-26) which will range from  $18 \times 1 = 18$  to  $18 \times 5 = 90$ .

The mobility subscore will be calculated as follows:

- Adult version: the sum of the scores from 13 questions (Questions 13, 15-24, 27 and 28) which will range from  $13 \times 1 = 13$  to  $13 \times 5 = 65$ ;
- Paediatric version: the sum of the scores from 8 questions (Questions 3, 4, 5, 12-15 and 20) which will range from  $8 \times 1 = 8$  to  $8 \times 5 = 40$ .

Missing scores for individual questions will not be imputed, but they will be taken into account according to the rules described below:

- (1) If more than 20% of the questions contributing to the total score are missing, the total score will not be calculated. It will be considered as missing;

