#### **Growth Status**

Height, bone age, skeletal maturity and epiphyseal status will be analysed for growing children (paediatric).

Linear height velocity, linear height z-scores, knee height velocity, and chronological age will be derived for growing children. Annualised height velocity will be derived once two consecutive measurements are spaced by a minimum of 6 months and a maximum of 12 months.

Actual values and changes from the Baseline Visit in linear height and knee height velocity and the difference between chronological age and bone age will be presented at each visit. Linear height z-scores and change from Baseline until final adult height (defined clinically as last height velocity <1cm/year or radiologically as closed epiphysis of hand-wrist or knee) is achieved will be presented at each visit. The frequency, severity and descriptive details of PPC in growing children will also be presented overall.

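### For participants already taking palovarotene at enrolment, change is measured from an on-treatment Baseline Visit, although values at the first marketed dose are collected

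*Protocol*

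**What the plan says.** **Reference point for change.** For CAJIS, section 9.7.3.3 reads "Actual values as well as the change from the Baseline Visit in CAJIS total score will be presented for each visit". It uses the Baseline Visit in the same way for assistive devices, FOP-PFQ, PROMIS and lung function. Section 9.7.3.4 (Growth Status) has "Actual values and changes from the Baseline Visit in linear height and knee height velocity", and 9.7.3.5 reports the shift in Tanner stage from the same visit. No exception is made for participants already on treatment.

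**Population.** For the effectiveness tables, 9.7.3.3 says "Analyses and summary tables will be presented in the Safety Exposed and the Safety Unexposed Populations".

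**Who is non-naïve.** Section 9.1 covers "All participants who received at least one dose of palovarotene treatment before enrolling in the registry study", with enrolment meaning signature of the consent form. The Baseline Visit belongs to enrolment (9.2.7.1).

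**What is collected earlier.** In Table 3, note p reads "Retrospective data collected only at the first marketed palovarotene intake". It is attached to CAJIS, spirometry/DLCO, growth status and Tanner staging, among others. Section 9.2.7.1 agrees: "CAJIS for FOP at the first marketed palovarotene intake and at the Baseline Visit". Height is also sought from 6 to 12 months before first marketed dose (Table 3, note f).

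**Time origin elsewhere.** The comparison in 9.7.3.4 sets Day 1 at first marketed dose for naïve and non-naïve exposed participants alike.

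**User type.** Section 9.7.1 defines prevalent and incident users and says they will be distinguished. Section 9.7.3.3 does not take this up, and 9.7.4 names only age group and gender as subgroups.

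**The concern.** A change-from-Baseline table for a treated cohort is normally read as change since treatment began. Here that reading is right for a participant who starts palovarotene at enrolment and wrong for one who enrols after months or years on it. The second participant's reference value already contains whatever happened on treatment up to consent.

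If both kinds of participant share one column, the mean is neither pre-post change nor later on-treatment change, and a reader cannot tell how much of each it contains. The protocol plans to collect the values that would avoid this and already uses the better time origin in another analysis. The same people therefore have two starting points in one plan. Describing effectiveness in exposed participants is the study's second stated aim (8.1), so these tables matter to the report.

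**Working it through.** The protocol states no figure that depends on this choice, so there is nothing to reproduce. The check is a comparison of sections, followed by an illustration on assumed inputs.

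**Step 1: sections side by side (non-naïve participants).**

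| Measure | Value planned at first marketed dose? | Reference used for change |
|---|---|---|
| CAJIS | Yes (Table 3 note p; 9.2.7.1) | Baseline Visit (9.7.3.3) |
| Lung function | Yes (same) | Baseline Visit (9.7.3.3) |
| Linear height velocity | Height from first dose, plus one value 6–12 months earlier (Table 3 note f; 9.2.7.1) | Baseline Visit (9.7.3.4) |
| Knee height velocity | Knee height at first dose (note p) | Baseline Visit (9.7.3.4) |
| Tanner stage | Yes (note p; 9.2.7.1) | Baseline Visit (9.7.3.5) |
| FOP-PFQ, PROMIS, assistive devices | Yes in 9.2.7.1, no entry in Table 3 | Baseline Visit (9.7.3.3) |

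Linear height z-score is left out of the claim. Section 9.7.3.4 refers its change to Baseline without naming the visit.

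**Step 2: how much is left out for one prevalent user.** Let T be years treated before the Baseline Visit and F years followed after it. Neither is given, so both are assumed. If change is linear in time on treatment, the share left out is T/(F+T).

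| | F = 1 | F = 2 | F = 5 |
|---|---|---|---|
| T = 0.5 | 33% | 20% | 9% |
| T = 1 | 50% | 33% | 17% |
| T = 2 | 67% | 50% | 29% |
| T = 3 | 75% | 60% | 37.5% |

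The extremes are 0.5/5.5 = 9% and 3/4 = 75%.

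**Step 3: what pooling does.** Let f be the non-naïve share, e the mean change in the first year on treatment, and l the mean change in a later year. All three are assumed. The pooled change one year after the Baseline Visit is (1−f)e + f·l.

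- e = 0 and l = 0.5 CAJIS points: f = 0.25, 0.50, 0.75 gives 0.125, 0.25, 0.375.
- e = 1 and l = 0.5: the same f gives 0.875, 0.75, 0.625.
- e = l = 0.5: the result is 0.5 whatever f is.

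Pooling can therefore move the figure either way. It does not distort the yearly rate when early and later change are equal. The change before enrolment (Step 2) is left out in every case.

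**Step 4: related wording that does not agree.**

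- Section 9.1 makes any earlier palovarotene dose non-naïve, without restricting this to marketed product. Table 2 and 9.2.7.1 nevertheless list "Prior use of palovarotene (investigational product" among the items recorded for naïve participants.
- For CAJIS, 9.3.2.8 says "The CAJIS for FOP will be collected at the Baseline Visit and at the Follow-up/End of Study Visits" and omits the first-dose value that Table 3 and 9.2.7.1 call for. The lung function text in 9.3.2.8 has the same gap.
- Table 3 and 9.2.7.1 differ on first-dose questionnaires, as shown in Step 1.

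**The case against.** The best defence is that 9.7.3 calls itself a summary, with detail left to a separate SAP. Section 9.7.1 promises to distinguish prevalent from incident users, so the SAP may well give separate columns. That stands as far as pooling goes, which is why mixing is stated here only as conditional. It does not answer the first part. The protocol itself fixes the Baseline Visit as the reference, and separate columns would still leave prevalent users without a pre-treatment value.

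It is also fair that the earlier data are not lost. Growth from first marketed dose enters the exposed/unexposed comparison, CAJIS at the index date enters the propensity model, and effectiveness data go into the listings. A reader might infer that early growth slowing vanishes from the study. It does not; it is missing from the change-from-Baseline-Visit tables.

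Other stronger readings also lack support:

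- **Pooled change shrinks in proportion to the non-naïve share.** That needs change after consent to be near zero, and the protocol gives neither the share nor any such figure.
- **A child enrolling after 18 months must show no change in height velocity.** Section 7.3.1 gives 12 to 18 months as the typical timing of premature physeal closure under chronic dosing only. It reports none in 38 participants aged 14 to under 18, and gives no loss of height velocity.
- **The 164 participants exposed in trials are a pool that will transfer.** This is a count of past exposure; nothing says how many could enrol.
- **Former trial participants will be classed as naïve.** Section 9.1 read literally makes them non-naïve. The Table 2 item is a conflict to resolve, not evidence of misclassification.

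Lastly, first-dose values come from routine records and will sometimes be absent. That calls for a rule on missing reference values; it does not justify an on-treatment one.

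**Conclusion.** The point holds for CAJIS, lung function, linear and knee height velocity, and Tanner stage. For prevalent users the stated reference is an on-treatment value, while an earlier one is planned for collection and first marketed dose is already Day 1 in the comparison. The change tables leave out these participants' change before enrolment. Unless 9.7.1 is carried through, they also combine two different quantities.

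The size cannot be determined from the protocol. The 9% to 75% range applies to one prevalent user and rests on linear change and on the assumed T and F. No figure can be given for the pooled mean without the non-naïve share and the early and later rates of change.

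No hypothesis is tested and no error rate is affected. What is at risk is how the descriptive effectiveness and growth tables are read. This should be corrected, but it does not threaten the primary safety objective.

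**What to change.** 1. For exposed participants, define Baseline for CAJIS, lung function, growth measures and Tanner stage as the last available value at or before first marketed dose, and report how many have none.
2. Carry the prevalent/incident distinction of 9.7.1 into these tables and present results by time since first marketed dose. Moving Baseline alone is not enough. If visits are still counted from enrolment, the first follow-up could be months after Baseline for one participant and years after it for another.
3. For prevalent users, show change since the Baseline Visit separately under a label such as *change since enrolment*. Treat the questionnaires the same way unless first-dose values exist.
4. Reconcile 9.1 with Table 2 and 9.2.7.1 on prior investigational palovarotene in naïve participants, Table 3 with 9.2.7.1 on first-dose questionnaires, and 9.3.2.8 with Table 3 and 9.2.7.1 on first-dose CAJIS and lung function.

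The definition in item 1 would also serve unexposed participants who start palovarotene and stay in the registry. Section 9.2.8 moves them to the naïve schedule, but 9.7.3.3 sets no new Baseline for them.

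The cost is revised text, visit windows based on time since first dose and somewhat more tables. No new data are needed for the measures in item 1. The downside is more missing Baseline values among prevalent users.

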**PAGE 57 OF 287** 

form (developed for participants 8 to 14 years old) and a proxy-completed paediatric form (developed for participants 5 to 14 years old).

The FOP-PFQ consists of 28 questions in the adult version and 26 questions in the paediatric version which are scored on a scale of 1 to 5, with lower scores indicating that the participant has more difficulty completing those tasks. Score calculations are described in Section 9.7.3.3.

PROMIS Global Health Scale is a patient-reported outcome measure of physical and mental function in participants ≥15 years old and overall QoL for participants <15 years old. There are adult and paediatric versions of the PROMIS Global Health Scale; the adult form should be used for participants 15 years and older and for participants under 15 years old, there is a self-completed paediatric form (developed for participants 8 to 14 years old) and a proxy completed paediatric form (developed for participants <15 years old).

The PROMIS Global Health Scale consists of 10 questions in the adult version and 9 questions in the paediatric version. For the adult form, two scores are calculated: the global physical health score and the global mental health score, both ranging from 4 (worse health) to 20 (better health). For the paediatric form, only a total score is calculated, ranging from 7 (worse health) to 35 (better health). All scores are converted to T-scores, with a higher T-score value indicating better health. Score calculations and conversion to T-scores are described in Section 9.7.3.3.

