- (2) If less than 20% of the questions contributing to the total score are missing, the total score will be calculated by summing all observed question scores, divided by the number of questions that were answered and by multiplying this average score by the total number of questions that were meant to be answered (i.e. × 28 for the adult version and × 26 for the paediatric form).

The two rules described above also apply to the upper extremities subscore and the mobility subscore.

As the analysis for FOP-PFQ will be performed across all participants (paediatric and adult) and the number of contributing questions differs, the scores will be transformed to reflect a percentage of worst score. The percentage of worst score ranges from 0% to 100% with 0% indicating the best possible function and 100% indicating the worst possible function.

The % of worst scores (for total score, upper extremities subscore and mobility subscore) as well as the change from the Baseline Visit will be presented for each visit overall and by age group.

PAGE 63 OF 287

Patient-Reported Outcomes Measurement Information System Global Health Scale

For the adult version, the global physical health and global mental health scores will be calculated as follows:

- Global physical health scores will be calculated as the sum of scores from Questions 3, 6, 7 and 8 and will range from 4 (worse health) to 20 (better health);
- Global mental health scores will be calculated as the sum of scores from Questions 2, 4, 5 and 10 and will range from 4 (worse health) to 20 (better health).

In the calculation of the above scores, the Question 7, 8 and 10 will be rescaled as shown in Table 5.

If a participant is missing any of the contributing raw scores, the corresponding score (global physical health or global mental health score) will not be calculated for that participant.

Raw Score Questions **Rescaled Score** 0 1-3 4 4-6 7-9 10 1 8 and 10 5 1 4 2 3 3 4 2

 Table 5
 Rescaled Global Physical and Mental Health Scores for the Adult Version of PROMIS

PROMIS=Patient-Reported Outcomes Measurement Information System

For the paediatric version, the total score will be calculated as the sum of scores from the first 7 questions and will range from 7 (worse health) to 35 (better health).

If more than 3 questions contributing to the total score are missing, the total score will not be calculated. It will be considered as missing.

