If not more than 3 questions contributing to the total score are missing, the total score will be calculated by summing all observed question scores, divided by the number of questions that were answered and by multiplying this average score by the total number of questions that were meant to be answered (i.e.  $\times$  7).

The global physical health score, the global mental health score and the total score will also be converted into T-scores. T-score distributions are standardised such that a value of 50 represents the average (mean) for the general population and increments of  $\pm 10$  points represent  $\pm 1$  standard deviation away from the norm. Higher T-scores indicate better physical/mental health. A T-score <50 indicates worse health than the general population, while a T-score >50 indicates better health.

For example, a participant who has a T-score of 60 is 1 standard deviation better (healthier) than the general population. Conversion tables are provided in Appendix 2.

Actual values as well as the change from the Baseline Visit in mean global physical and mental health score converted into T-scores (for participants ≥15 years old) and mean total score converted into T-scores (for participants <15 years) will be presented for each visit overall and by age group.

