**PAGE 102 OF 287** 

**Appendix 2 CONVERSION TABLES OF PROMIS RAW SCORE INTO T-SCORES** 

**PAGE 103 OF 287** 

Table 6 PROMIS T-Score Conversions for Adult Global Physical and Mental Health

Adu	lt Global Physica	ıl Health	Adult Global Mental Health		
Raw Score	T-Score	Standard Error	Raw Score	T-Score	Standard Error
4	16.2	4.8	4	21.2	4.6
5	19.9	4.7	5	25.1	4.1
6	23.5	4.5	6	28.4	3.9
7	26.7	4.3	7	31.3	3.7
8	29.6	4.2	8	33.8	3.7
9	32.4	4.2	9	36.3	3.7
10	34.9	4.1	10	38.8	3.6
11	37.4	4.1	11	41.1	3.6
12	39.8	4.1	12	43.5	3.6
13	42.3	4.2	13	45.8	3.6
14	44.9	4.3	14	48.3	3.7
15	47.7	4.4	15	50.8	3.7
16	50.8	4.6	16	53.3	3.7
17	54.1	4.7	17	56	3.8
18	57.7	4.9	18	59	3.9
19	61.9	5.2	19	62.5	4.2
20	67.7	5.9	20	67.6	5.3

PROMIS=Patient-Reported Outcomes Measurement Information System

PAGE 104 OF 287

 Table 7
 PROMIS T-Score Conversions for Paediatric Global Health

Paediatric Self-Completed Total			Paediat	ric Proxy-Com	oleted Total
Raw Score	T-Score	Standard Error	Raw Score	T-Score	Standard Error
7	16	3.4	7	14.7	2.9
8	17.1	3.6	8	15.3	3.1
9	18.3	3.7	9	16	3.2
10	19.7	3.8	10	16.9	3.4
11	21.2	3.8	11	18.1	3.6
12	22.8	3.7	12	19.4	3.7
13	24.4	3.6	13	21	3.8
14	26.1	3.6	14	22.7	3.8
15	27.6	3.5	15	24.4	3.7
16	29.2	3.5	16	26.1	3.7
17	30.8	3.5	17	27.7	3.7
18	32.4	3.6	18	29.4	3.8
19	34	3.6	19	31.2	3.8
20	35.6	3.6	20	32.9	3.8
21	37.2	3.6	21	34.6	3.8
22	38.8	3.6	22	36.2	3.8
23	40.4	3.6	23	37.9	3.9
24	42.1	3.7	24	39.7	4
25	43.9	3.7	25	41.7	4
26	45.7	3.6	26	43.6	3.9
27	47.5	3.6	27	45.4	3.8
28	49.2	3.6	28	47.3	3.9
29	51.1	3.7	29	49.3	4.1
30	53.3	3.9	30	51.8	4.4
31	55.7	4.2	31	54.5	4.7
32	58.3	4.5	32	57.3	5
33	61.1	4.9	33	60.2	5.4
34	64.2	5.4	34	63.2	6
35	67.5	6.1	35	66.1	6.5

PROMIS=Patient-Reported Outcomes Measurement Information System

IPSEN GROUP CLIN-60120-453

CONFIDENTIAL

REGISTRY STUDY PROTOCOL: VERSION 8.0: DATE 16 APRIL 2025 PAGE 105 OF 287

CCI

[figure not shown]

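### FOP-PFQ total: change from Baseline is pooled across the paediatric and adult forms, so a child who turns 15 can show a change that comes from the form's item mix

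*Protocol*

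**What the plan says.** Form by age. Section 9.3.2.8 says for the FOP-PFQ that "the adult form should be used for participants 15 years and older"; below that age there are self-completed and proxy-completed paediatric forms.

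Item content. Section 9.7.3.3 lists the questions behind each subscore. For the upper extremities it gives "Paediatric version: the sum of the scores from 18 questions", against 15 questions on the adult form. Mobility has 8 paediatric and 13 adult questions. The totals have 26 and 28.

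Pooling. Section 9.7.3.3 states that the FOP-PFQ is analysed across children and adults together and that, because "the number of contributing questions differs, the scores will be transformed to reflect a percentage of worst score". For the total and both subscores, the percentages "as well as the change from the Baseline Visit will be presented for each visit overall and by age group". No sentence excludes, flags or re-baselines a participant whose form has changed since Baseline, and section 9.9 (limitations) does not mention it.

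PROMIS. Participants of 15 and over have physical and mental T-scores. For younger participants, the "mean total score converted into T-scores (for participants <15 years) will be presented for each visit overall and by age group". Appendix 2, Table 7 has separate self-completed and proxy-completed conversions.

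**The concern.** The protocol gives one reason for rescaling, the unequal number of questions, and the rescaling answers only that. Putting two totals on a 0-100% range does not make them measure the same mixture of abilities. The adult total gives mobility about half as much weight again as the paediatric total does.

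A participant with a paediatric-form Baseline and adult-form follow-up therefore has a change in total that combines disease course with a change of weights. Describing effectiveness, including the effect on physical function, is the registry's second stated aim, and the FOP-PFQ is its disease-specific measure of physical function. About half of each cohort is to be paediatric and the study may run for 11 years, so such participants will not be rare. The display by age group does not remove the problem: a participant who has crossed 15 is still measured against a paediatric-form Baseline.

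**Working it through.** **Reproducing the plan's figures.** The listed question numbers give 15 upper-extremity and 13 mobility items on the adult form (28), and 18 and 8 on the paediatric form (26). On each form the two lists cover every question once, with no overlap. The stated ranges follow as n × 1 to n × 5: totals 28-140 and 26-130.

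**Percentage of worst score.** The protocol states the 0-100% range but no formula. As lower item scores mean more difficulty, I use 100 × (maximum − score)/(maximum − minimum) = 100 × (5n − score)/(4n).

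**Shift at the switch.** Let U and M be the upper-extremity and mobility % of worst score, the same on both forms.

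- Paediatric total = (18U + 8M)/26, so mobility weight = 8/26 = 30.8%.
- Adult total = (15U + 13M)/28, so mobility weight = 13/28 = 46.4%.
- Adult minus paediatric = (13/28 − 8/26) × (M − U) = 0.157 × (M − U).

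| U | M | Paediatric total | Adult total | Shift (points) |
|---|---|---|---|---|
| 20 | 50 | 29.2 | 33.9 | +4.7 |
| 20 | 70 | 35.4 | 43.2 | +7.8 |
| 50 | 20 | 40.8 | 36.1 | −4.7 |
| 75 | 25 | 59.6 | 51.8 | −7.8 |
| 40 | 40 | 40.0 | 40.0 | 0 |

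A positive shift looks like worsening. The fourth row corresponds to item means of 2 (upper extremity) and 4 (mobility); reversing them gives 40.4 and 48.2.

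**How many cross 15.** Inputs from the protocol: 67 + 33 = 100 participants, about half paediatric (about 50); girls 8 to under 18, boys 10 to under 18; enrolment up to 10 years, study up to 11 years, at least 1 year of data. Assumptions of mine: ages evenly spread, half girls.

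- Share starting under 15: (7/10 + 5/8)/2 = 66%.
- 1 year of follow-up for all: (1/10 + 1/8)/2 = 11%, about 6 of 50.
- 5 years for all, no dropout: (5/10 + 5/8)/2 = 56%, about 28 of 50.
- Follow-up uniform over 1-11 years, no dropout: girls 5.2/10, boys 4.2/8, mean 52%, about 26 of 50.
- The same with 10% or 20% annual dropout (simulated): 40% or 31%, about 20 or 16 of 50.

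**The case against.** The strongest reply has four parts.

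- **The subscores protect the reader.** Section 9.7.3.3 also reports both subscores. In the model above they do not move at the switch, so a stable pair would sit beside a shifting total. This stands and limits the harm. It depends, however, on each domain reading the same on both forms, which nothing in the protocol establishes, and the total is still reported in its own right.
- **The size is unknown.** A 7.8-point shift needs a 50-point gap between domains, and the protocol gives no domain means or standard deviations. This also stands: the formula follows from the item lists, but the points are illustrations.
- **This is detail for the SAP.** Section 9.7.3 does defer technical detail. The pooling, the method of harmonising and its reason are nevertheless already fixed in the protocol, so the reply fails for the FOP-PFQ. It succeeds for PROMIS.
- **Nothing confirmatory depends on it.** These are secondary, descriptive endpoints, and the FOP-PFQ is not among the outcomes compared between cohorts in section 9.7.3.4. This stands; no error rate, sample size or primary result is touched.

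A reader might also infer two stronger points. The first is that PROMIS change is calculated across instruments at 15. The text does not say so: it defines separate scores by age, so a child who turns 15 simply has no matching Baseline score and the change is undefined. The second is that paediatric self and proxy reports alternate or are averaged, with a bias of 0.9 to 3.4 T-score points, the range of differences between the Table 7 columns at equal raw score. The protocol neither says they alternate nor that they are pooled. The gap reflects separate calibration of the two forms; it shows that the columns are not interchangeable and does not measure a bias.

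**Conclusion.** The point holds for the FOP-PFQ total. The protocol fixes a change from Baseline that crosses two forms with different domain weights, on a rationale that covers only the number of items. The resulting shift is 0.157 × (M − U) in either direction and vanishes only when the two domains are equally impaired. This assumes that each domain's % of worst score is equal on both forms and that the percentage is computed as above.

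It would go too far to say that most children who start under 15 will be affected. Dividing by the 66% who start under 15, the share of those who cross is about 17% with 1 year of follow-up and 47-79% with follow-up uniform over 1-11 years. The result turns on retention, and section 9.2.8 generally withdraws exposed participants who stop palovarotene. The problem merits correction because it concerns how physical function is described over time. For PROMIS the document shows no error, only an opening for a clarification.

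**What to change.** In section 9.7.3.3:

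1. Flag the form used at each FOP-PFQ assessment.
2. Make the main change summary the change from Baseline restricted to assessments on the same form as Baseline.
3. Show change after the switch separately, counted from the first adult-form assessment.
4. If a cross-form change in total is also shown, label it as not like-for-like and have it read alongside the subscores.
5. For PROMIS, state that change from Baseline is presented only within the same form and the same T-score table (self or proxy).

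The cost is a few sentences and a flag in the dataset; scoring already requires knowing which form was completed. The real price is shorter within-form follow-up for children who pass 15. Item 4 allows the long-run series to be kept, with a warning, so that the registry need not discard it.
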